1. An extended-release (30-day, “XR”), intramuscular injection of naltrexone (Vivitrol®). Studies on XR naltrexone have shown better long-term medication continuation compared to oral naltrexone and reduced heavy drinking days compared with placebos. Additionally, one meta-analysis showed a trend toward fewer admissions compared to oral naltrexone. One ongoing clinical trial is directly comparing oral to XR naltrexone for AUD in a safety-net hospital in Boston, and it is expected to evaluate the results in late 2020. Regardless, data from multiple centers and regions are needed, and our study uniquely targets high-utilizer patients.
2. A single infusion of intravenous ketamine, a dissociative anesthetic used in general anesthesia and pain management. At sub-anesthetic doses, ketamine provides rapid effects on mood that extend weeks beyond administration, and in 2019 the FDA approved an intranasal formulation for treatment-resistant depression. For AUD, treatment with ketamine decreased cravings and drinking at 10 days post-infusion in a human laboratory study that excluded patients with depression. In a recent randomized trial, AUD patients were given one ketamine infusion and subsequently showed a higher rate of abstinence at 21 days beyond treatment and better attendance at the final study visit compared to the control group (100% vs 74%, respectively), with no serious adverse events reported.

Both single-dose interventions hold great potential for improving AUD post-hospital transitions and reducing immediate re-admissions, but more data on feasibility and effectiveness are needed.

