Intervention administered [data collection point #2]	RN, ACS	
For 'linkage-alone' group, data to be entered following consult.
 
For NTX group, intervention administered prior to discharge (could be same day as consent). Vitals immediately preceding and 40 min post- injection. Data collected after administration.
 
For KET group, intervention administered prior to discharge (could be same day as consent), though should have no food for at least 3 hours (~50% gastric emptying). Vitals immediately preceding, after completion, and 2 hours following end of intervention.
	
 
Vital signs (HR, BP, O2): linkage-alone group- baseline only, recorded after consult. NTX group- baseline, 40 min after administration. KET group- baseline, end of administration (~40min), 2 hours after end of administration.
 
Most recent AST, ALT
 
UDS-5 data
 
[for KET] Dissociative symptoms (CADSS) after administration (40 min)
 
[for NTX and KET] Acceptability of intervention (10-point Likert) after administration
 
[for NTX and KET] Readiness to change (SOCRATES-8A) after administration (40 min)
 
 
ORDER: CMP (if not already obtained), UDS-5 (if not already obtained)
 
ORDER in discharge orders (outpatient): CMP, UDS-5, urine EtG (if not already ordered)

↓			
Presentation to SUDS, data entered, contingency management reward administered [data collection point #3]	SUDS staff	
Upon presentation, staff to collect study data. After completion, will receive contingency management reward.
 
Then patient to complete standard intake/follow-up visit, if willing.
	
 
Drinking History since discharge (TLFB since discharge)
 
Depression symptoms (PHQ9 modified to read "since discharge.")
 
Readiness to change (SOCRATES-8A)
 
[for KET] Dissociative symptoms (CADSS)
 
Adverse Events (Modified PRISE)
 
Acceptability of intervention (10-point Likert)
 

		Staff to instruct patient to present to the clinic laboratory (e.g. pav G) for CMP after the visit.	
 
Contingency management feedback (10-point Likert, open ended)
 

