30-day chart review [data collection point #4]	Research staff	Should check encounters tab as well as “care everywhere” for Denver Metro region.	
 
Admissions (up to 5) within 30 days of discharge date (date, location, up to top 3 main diagnoses based on documentation available).
 
ED visits (up to 5) within 30 days of discharge date (date, location, up to top 3 main diagnoses based on documentation available).
 
AST, ALT obtained at SUDS f/u (if available)
 
Urine EtG obtained at SUDS f/u (if available)
 

Screening: The addiction consult team will attempt to screen patients meeting the inclusion criteria during inpatient admission. We anticipate 10 patients will meet inclusion criteria weekly. They will be assessed for clear exclusion criteria documented in the chart, and if none are noted the patient will be asked if they would like to join the study and complete the screening. If still no exclusion criteria are met and the patient expresses interest, they will be engaged in informed consent. The primary team will be notified by the addiction medicine team. Each combined process of screening and consent is anticipated to require 15 minutes at the end of a typical consultation. The screening window is anticipated to last 5 months.

Randomization: Patients will undergo a simple randomization algorithm to one of three arms.

Intervention:

- **Arm 1:** Receive a single dose of XR naltrexone (380mg) prior to discharge.
- **Arm 2:** Receive a single infusion of IV ketamine (0.5 mg/kg over 40 minutes) prior to discharge.
- **Arm 3:** No single-dose medication
- *All groups will receive enhanced linkage to care that includes contingency management, initiation of biopsychosocial intake, and appointment scheduling. This aspect alone surpasses the current standard of care.*

Contingency Management: Patients will receive a debit card prior to discharge from the hospital. We will utilize a pre-existing system - ClinCard by Greenphire. Participants will receive \$10 upon completion of baseline data, and \$20 upon completion of follow-up data (at SUDS clinic).

Follow up: Patients will be assigned a follow-up within 7 days of discharge at the outpatient addiction clinic (Denver Health SUDS clinic in pavilion K).

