#### **D. Description, Risks and Justification of Procedures and Data Collection Tools:**

*Table 5 Overview of risks and justifications of procedures and data collection tools*

Procedure/Tool	Description, Risks	Justification
Injection of IM medication (naltrexone)	Risks include minimal pain and discomfort at the injection site which will occur on the lateral thigh or the buttock. One study suggested that the discomfort of an injection itself deterred a large number of participants.  If that is the case for our study, this decision will be honored with no repercussion aside from not enrolling in the study. More serious risks such as infection, blood clot, bleeding and/or allergic reaction are rare.	These risks are justifiable as there is very little risk of serious or permanent harm, and potential benefits in terms of preventing the consequences of heavy drinking are almost certainly greater.
Medication-related risks of naltrexone	Risk of opioid withdrawal if the patient is taking opioids concurrently (an exclusion criteria); Liver injury can be seen, but is usually mild and self-limiting. Patients with AST/ALT >5x ULN, hepatic failure, or decompensated cirrhosis will be excluded. Nausea, sleepiness and headache are the other most common medication side effects.	These risks are justifiable as there is very little risk of serious or permanent harm, and potential benefits in terms of preventing the consequences of heavy drinking. It is a single dose which limits exposure.
Medication-related risks of ketamine	Risk of unpleasant dissociative symptoms, delirium, hallucinations; high blood pressure which could lead to adverse cardiac events if patients are not screened carefully; initiation of ketamine abuse after discharge.	These risks are justifiable as there is very little risk of serious or permanent harm, and potential benefits in terms of preventing the consequences of heavy drinking. It is a single dose which limits exposure. Patients who experienced delirium during hospital stay will be excluded. Patients with known cardiovascular disease will be excluded. The most recent randomized trial using ketamine found no initiation of ketamine “abuse” following administration. 

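### After discharge, the only listed adverse-event form and scheduled liver test belong to a clinic visit assigned within 7 days, and the 30-day chart review has no stated adverse-event step

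*Combined protocol and SAP*

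**What the plan says.** Section II describes the naltrexone product as "An extended-release (30-day, “XR”), intramuscular injection of naltrexone". Section IV.D, Table 5, says of its risks that "Liver injury can be seen, but is usually mild and self-limiting". It also names opioid withdrawal and, as rare, infection, clot, bleeding or allergic reaction from the injection. Table 3 adds that naltrexone may worsen thrombocytopenia.

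Table 1 (Section IV.A) places adverse effects among the primary feasibility outcomes and gives chart review and questionnaires as the instruments for that row as a whole. Section IV.F compares adverse events between groups with Fisher's exact test.

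Table 4 (Section IV.C) sets out the collection:

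- **Point #2, around dosing:** "Most recent AST, ALT" and vital signs (for naltrexone, before and 40 minutes after injection). The Data Collection text adds that symptoms are recorded just after the intervention.
- **Point #3, SUDS visit:** "Adverse Events (Modified PRISE"), and "Staff to instruct patient to present to the clinic laboratory (e.g. pav G) for CMP after the visit". On timing, the plan states: "Patients will be assigned a follow-up within 7 days of discharge at the outpatient addiction clinic".
- **Point #4, 30-day chart review:** up to five admissions and five ED visits, each with date, location and up to three diagnoses; urine EtG from the SUDS visit; and "AST, ALT obtained at SUDS f/u (if available").

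**The concern.** Solicited adverse events and the one scheduled post-dose liver test fall early in the stated 30-day life of the depot. The later look, at day 30, is aimed at utilization. Point #4 lists no adverse-event, seriousness or relatedness item, and it restricts AST/ALT to the SUDS result even though the abstractor is already in the chart. Platelets are named in no follow-up order or extraction item.

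Take a naltrexone patient re-admitted on day 20 with raised enzymes or an injection-site abscess. That patient enters Aim 2 as a re-admission. No described step enters the same patient in the Aim 1 adverse-event comparison, and the enzyme values from that stay are not listed for abstraction.

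At stake is a primary feasibility outcome that is meant to inform a larger trial. In arms of about 15 to 20, whether one or two such patients are classified as having had an adverse event alters the safety comparison. Ketamine is touched as well, since Table 5 names the start of ketamine misuse after discharge as a risk.

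**Working it through.** The plan states no figure for this point, so there is none to reproduce. The check sets the tables side by side and then sizes the gap.

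**Step 1. Table 1 against Table 4.** Table 1 says chart review contributes to a row that includes adverse effects. Table 4, the operational schedule, lists four items for the chart review: admissions, ED visits, AST/ALT from the SUDS visit, and EtG from the SUDS visit. None is an adverse-event item. The tables do not say how chart review would supply adverse events.

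**Step 2. Time not covered.** Inputs: 30 days (Section II); a visit assigned within 7 days of discharge (Section IV.C, Follow up). Assumption: dosing is close to discharge, as Section IV.C intends. Uncovered share = (30 − visit day)/30.

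- Visit on day 7: (30 − 7)/30 = 23/30 = 77%.
- Visit on day 3: 27/30 = 90%.
- Visit on day 14: 16/30 = 53%.

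The range matters because 7 days is an appointment target and no outer limit is given for the actual visit. Uncovered here means without an adverse-event form or a scheduled liver test. Admission and ED diagnoses are still recorded through day 30.

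**Step 3. Patients who miss the visit.** They have no PRISE and no scheduled liver result after discharge. Attendance in this trial is unknown. The historical figure in Sections II and III is 2 of 17 = 11.8% (exact 95% CI 1.5% to 36.4%), without the incentives planned here. Expected forms per arm = (N/3) × attendance, with N = 45 to 60 and equal arms assumed (simple randomization gives this only on average):

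| Attendance (assumed) | N = 45 (15 per arm) | N = 60 (20 per arm) |
|---|---|---|
| 11.8% | 1.8 | 2.4 |
| 50% | 7.5 | 10 |
| 100% | 15 | 20 |

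**Step 4. Naltrexone patients re-admitted within 30 days.** Section IV.F assumes 25% against 15%. Section I hypothesizes lower rates on medication, so 15% is the medication-arm rate. 15 × 0.15 = 2.25 and 20 × 0.15 = 3.0, or about 2 to 3 patients. The 25% rate (up to 20 × 0.25 = 5) belongs to linkage-alone, which receives no study drug.

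**The case against.** Several stronger readings are tempting, and the documents do not support them.

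- A reader might infer that safety is looked at only at the clinic visit. It is not: AST/ALT, vital signs and symptoms are also recorded around dosing. The gap concerns the period after discharge.
- A reader might infer that later liver results are thrown away. They are not listed for abstraction; nothing says they are discarded.
- A reader might infer that a day-20 re-admission is ruled out as an adverse event. No such rule is written. Its diagnoses would be in the dataset by arm, so an abscess or liver injury among the three recorded could be found. What is missing is a stated step to classify it.
- A reader might take 77% of days as 77% of harms. The documents give no release profile or time to onset, and Table 5 calls the serious injection risks rare. The amount of harm missed cannot be sized.
- A reader might link the 30-day opioid exclusion in Table 3 to the depot's duration. The stated rationale is only that naltrexone blocks opioids.

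There is also a fair case against over-collecting in a single-dose pilot. Laboratory values taken from any encounter come mostly from patients who are re-admitted, so ascertainment depends on the primary clinical outcome. In this population such values are hard to attribute. Relatedness has no meaning in the linkage-alone arm and is judged open-label in the others. These limits stand and shape the fix.

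They do not close the gap. Section IV.E relies on chart review for re-admission precisely because it does not require clinic attendance. Adverse effects, also primary, have no equivalent stated safeguard.

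**Conclusion.** The point holds as a defect in adverse-event ascertainment after discharge and as a mismatch between Tables 1 and 4. Followed as written, Table 4 leaves events after the SUDS visit, and every post-discharge event in patients who miss it, out of the adverse-event comparison except as utilization.

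Its size is about 23 of 30 days without an adverse-event form or scheduled liver test, if the visit is on day 7 and dosing is near discharge. About 2 to 3 naltrexone patients would be re-admitted without a stated adverse-event review, assuming the plan's 15% rate and 15 to 20 patients per arm. The direction is toward under-counting late events; the number of events missed cannot be estimated from the documents. The plan should be changed before data collection. This is a matter of data collection and reporting, and it implies no change to clinical management.

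**What to change.** Reconcile Tables 1 and 4 by amending data point #4:

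1. For every admission and ED visit already abstracted to day 30, and any death found in the chart, record in all three arms whether it is an adverse event, with flags for the risks the protocol names. Record relatedness in the two medication arms only, and note that it is judged open-label.
2. Abstract any dated AST/ALT, and platelets if present, from dosing to day 30 from any encounter. Report these descriptively with the number tested per arm. Do not test them between arms, because being tested depends on returning to care.
3. Report PRISE events at the SUDS visit and chart-found events to day 30 separately, by arm, and state the ascertainment window and source for each.

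**Cost:** a few extra REDCap fields on a chart review already planned for every participant, with no new visit or test. Chart-found events are less complete than a questionnaire, reported counts will rise, and the laboratory values will come mainly from patients who return to care.

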#### **D. Description, Risks and Justification of Procedures and Data Collection Tools:**

*Table 5 Overview of risks and justifications of procedures and data collection tools*

Procedure/Tool	Description, Risks	Justification
Injection of IM medication (naltrexone)	Risks include minimal pain and discomfort at the injection site which will occur on the lateral thigh or the buttock. One study suggested that the discomfort of an injection itself deterred a large number of participants.  If that is the case for our study, this decision will be honored with no repercussion aside from not enrolling in the study. More serious risks such as infection, blood clot, bleeding and/or allergic reaction are rare.	These risks are justifiable as there is very little risk of serious or permanent harm, and potential benefits in terms of preventing the consequences of heavy drinking are almost certainly greater.
Medication-related risks of naltrexone	Risk of opioid withdrawal if the patient is taking opioids concurrently (an exclusion criteria); Liver injury can be seen, but is usually mild and self-limiting. Patients with AST/ALT >5x ULN, hepatic failure, or decompensated cirrhosis will be excluded. Nausea, sleepiness and headache are the other most common medication side effects.	These risks are justifiable as there is very little risk of serious or permanent harm, and potential benefits in terms of preventing the consequences of heavy drinking. It is a single dose which limits exposure.
Medication-related risks of ketamine	Risk of unpleasant dissociative symptoms, delirium, hallucinations; high blood pressure which could lead to adverse cardiac events if patients are not screened carefully; initiation of ketamine abuse after discharge.	These risks are justifiable as there is very little risk of serious or permanent harm, and potential benefits in terms of preventing the consequences of heavy drinking. It is a single dose which limits exposure. Patients who experienced delirium during hospital stay will be excluded. Patients with known cardiovascular disease will be excluded. The most recent randomized trial using ketamine found no initiation of ketamine “abuse” following administration. 
Data collection tools – questionnaires, urine Etg	All questionnaires have the potential to bring up unpleasant memories of their use and strong emotions related to their motivations to change. Gathering re-admission data from insurance claims has	These risks are justifiable as strict precautions to safeguard protected health information will be applied.

	the potential for a breach of confidentiality. However, precautions to safeguard protected health information in accordance with international standards for human subjects research will be applied.	
--	---	--

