### **B. Description of Population to be Enrolled:**

See Table 2 and 3 for inclusion and exclusion criteria. Rationales are also listed.

*Table 2 Inclusion criteria*

	INCLUSION criteria	Rationale
	Age 18-65	Limiting study scope to adult patients
	1+ alcohol-related* admission(s) OR 2+ alcohol-related ED visits in past 12 mo.  *Admission diagnoses includes any of following: - alcohol use / intoxication - alcohol withdrawal - alcohol use disorder / dependence - seizure thought to be related to alcohol withdrawal - encephalopathy thought to be related to alcohol - pancreatitis thought to be related to alcohol - liver disease thought to be related to alcohol - cardiac arrhythmia or heart failure thought to be related to alcohol - gastrointestinal bleed thought to be related to alcohol	Limiting study scope to high-utilizer patients
	Has insurance (public or private)	Can follow-up at SUDS clinic
	Seen by addiction consult	Part of recruitment plan

*Table 3 Exclusion criteria*

	EXCLUSION criteria	Rationale
	Known or suspected active COVID-19 infection	Staff safety and ability to immediately follow up at SUDS clinic

	Hepatic: AST/ALT >5x upper-limit of normal, decompensated liver failure	Naltrexone can rarely cause hepatotoxicity. 5x ULN used by study by Collins et al (2015)
	Renal: Glomerular filtration rate <30ml/min	Naltrexone not recommended in renal failure
	Cardiovascular: History of acute coronary syndrome, cerebrovascular event, hypertensive crisis, known cardiomyopathy	Ketamine can transiently raise blood pressure
	Known elevated intracranial pressure	Ketamine can transiently raise blood pressure
	Thrombocytopenia (<50/microliter)	Naltrexone can potentially worsen thrombocytopenia
	Active moderate/severe withdrawal (based on hospital withdrawal protocol)	May need acute care that would interfere with intervention and discharge planning
	Active delirium (alcohol-related or otherwise)	Ketamine's dissociative effects could theoretically worsen delirium
	Already enrolled in study	A-priori decision to only enroll patients once
	XR naltrexone or IV ketamine in last 30 days	Prior administration could affect ability to distinguish effect of current intervention. Recent receipt of intervention would also be evidence that intervention not effective for them.
	Known intolerance to naltrexone or ketamine	Avoid harm to patient
	Other active severe substance use disorder (tobacco, cannabis excluded)	Limiting study scope to AUD

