### C. Study Design and Research Methods

We propose an open-label, pilot feasibility trial (n=45-60), randomizing hospitalized patients to receive XR naltrexone, IV ketamine, or neither prior to hospital discharge, along with enhanced linkage to care. The primary clinical

outcome compared across each of the groups will be 30-day re-admission rates ascertained by chart review (Table 1).

To reduce variability, all participants will undergo a standard addiction consultation that includes behavioral components such as supportive therapy and motivational interviewing. They will also receive enhanced linkage to care (hereon “linkage”) which includes being met by a staff member while in the hospital to begin the clinic intake process and assign a follow-up appointment date. Linkage will also include a contingency management (monetary incentive to follow-up) in their post-hospital transition and receive standard case management and counseling at Substance Use Disorder Services (SUDS) clinic.

ACS team members will identify patients meeting inclusion criteria (Table 2), and – after conducting their usual consultation – approach them about the study. Approximately 900 patients met similar inclusion criteria in 2019 (Query by [name]). After screening for exclusion criteria, informed consent will occur, and initial baseline data will be obtained by “Treatment on Demand” (TOD), a grant-funded team of counselors who are already linking hospitalized patients to addiction care. Consented patients will then be randomized, and the ACS will work with the primary team to order and administer the assigned intervention close to discharge. Meanwhile, a TOD counselor will work to establish a follow-up date within seven days post-discharge. Additional data will be collected immediately after the intervention (for those in one of the two medication groups), at SUDS follow up, and 30-days post-discharge by chart review.

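### Table 5 justifies ketamine by excluding anyone who had delirium during the stay, but Table 3, the exclusion list, removes only patients with active delirium

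*Combined protocol and SAP*

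**What the plan says.** Section IV.B of the combined protocol and SAP says where eligibility is defined: "See Table 2 and 3 for inclusion and exclusion criteria. Rationales are also listed". In Table 3 the delirium row reads "Active delirium (alcohol-related or otherwise", and its rationale is that dissociation under ketamine might in theory make delirium worse. The cardiovascular row reads "Cardiovascular: History of acute coronary syndrome, cerebrovascular event, hypertensive crisis, known cardiomyopathy", with the rationale that ketamine can briefly raise blood pressure.

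In section IV.D, the ketamine row of Table 5 lists delirium among the risks, along with "high blood pressure which could lead to adverse cardiac events if patients are not screened carefully". It then justifies accepting these risks partly on the ground that "Patients who experienced delirium during hospital stay will be excluded. Patients with known cardiovascular disease will be excluded".

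Section IV.C has the addiction consult team and the primary team "order and administer the assigned intervention close to discharge". Table 4 calls for a formal check of the exclusion criteria before randomisation.

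**The concern.** Table 5 is where the protocol explains why giving ketamine to these inpatients is acceptable, and who is kept out is part of that explanation. If the exclusion list does not keep those people out, the protocol claims a safeguard that its eligibility rules do not deliver. For delirium the difference is one of time window: Table 5 looks back over the whole stay, while Table 3 looks only at the patient's present state. Two screeners, one relying on each table, would reach different decisions about the same patient.

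The matter concerns participant safety and consistent screening. It changes no statistical calculation. It does bear on who is exposed, and adverse effects are among the primary feasibility outcomes in Table 1.

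**Working it through.** The plan states no figure on this point, so the check is mainly a comparison of texts.

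**Delirium**

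| Patient | Table 3 | Table 5 |
|---|---|---|
| Delirious at screening | Excluded | Excluded |
| Delirious earlier in this stay, now resolved | Not excluded | Excluded |
| No delirium in this stay | Not excluded | Not excluded |

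The tables disagree on the middle row. Three checks follow.

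1. *Can such a patient arise?* Yes. The intervention is given near discharge, which leaves time for delirium to clear before screening and dosing.
2. *Does another exclusion catch the patient?* Not reliably. The withdrawal row, "Active moderate/severe withdrawal (based on hospital withdrawal protocol", is also limited to a current state. The psychiatric row concerns active psychosis and active suicidality. No other row of Table 3 mentions delirium.
3. *Does any other text bring in the wider rule?* No. The screening text in section IV.C and Table 4 refers to the exclusion criteria without adding to them.

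**Cardiovascular disease (secondary)**

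Read literally, the Table 5 term covers more than the four conditions in Table 3. Known arrhythmia, and stable coronary disease with no past acute coronary syndrome, fall under the term but are not named in the row. Table 2 counts "cardiac arrhythmia or heart failure thought to be related to alcohol" among its qualifying diagnoses, so patients with a known arrhythmia can be expected among those screened. Some heart failure would probably be caught by the cardiomyopathy item.

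**Size of the ketamine arm**

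Inputs: n = 45 to 60 (sections I and IV.C); three arms with simple randomisation (section IV.C). Equal allocation probability of 1/3 is assumed, because the protocol does not state a ratio.

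- Expected size = n/3: 45/3 = 15 and 60/3 = 20.
- Standard deviation = √(n × 1/3 × 2/3): √10 = 3.16 at n = 45 and √13.33 = 3.65 at n = 60.
- Mean ± 1.96 SD: 15 ± 6.2, roughly 9 to 21, and 20 ± 7.2, roughly 13 to 27.

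These figures describe the whole ketamine arm. The share of it with resolved delirium is not given and cannot be estimated from the documents.

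**The case against.** The strongest reply is that Table 5 is an overview and Table 3 is the operative list, so Table 5 should be read as a loose summary. There is some support for this. The naltrexone row of Table 5 also rephrases its liver exclusion rather than repeating it exactly. For the cardiovascular sentence the reply is persuasive: Table 3 labels the row as cardiovascular and then itemises it, so the Table 5 phrase can be read as the name of that row.

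It is less persuasive for delirium. Delirium during the stay is not a shorter way of saying active delirium; it covers a different period. The naltrexone row also keeps the same liver-enzyme threshold as Table 3, which gives a reader reason to take the ketamine sentences at face value.

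A second reply is that the Table 3 rationale, worsening of delirium, fits an active-only rule, and that nothing in the documents shows a risk at this dose once delirium has cleared. That stands, and it is why correcting Table 5 is an acceptable remedy. A bedside physician or investigator, and vital signs before, at the end of and 2 hours after the infusion, also limit the consequences, but they do not keep these patients out.

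Third, the screening form is not reproduced. That it follows Table 3 is an inference.

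A reader might go further and infer that the Table 2 arrhythmia entry contradicts Table 5. It does not. A patient can meet an inclusion criterion and still be removed by an exclusion, and the documents do not say that arrhythmia adds to the blood-pressure risk behind the cardiovascular row.

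**Conclusion.** The delirium mismatch is real and nothing elsewhere in the protocol resolves it. Under Table 3 as written, a patient whose delirium has resolved can be randomised to ketamine, while Table 5 counts that patient's exclusion as part of the case for accepting the risk. The wording should be corrected.

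The cardiovascular mismatch is a request for clarification. A reader might infer that a second safeguard is definitely missing, but the text also allows the shorthand reading.

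The number of affected patients is unknown and no harm rate can be derived. A reader might take 15 to 20 as the number exposed or as an upper limit. It is neither: it is the expected size of the whole ketamine arm under an assumed equal allocation probability, and simple randomisation lets the arm come out larger or smaller.

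The conclusion rests on Table 3 being the list that screeners apply, as section IV.B indicates.

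**What to change.** **Delirium.** Change the Table 3 row, and the screening form, to *delirium at any time during this hospital stay*. The cost is one row of wording and slightly fewer eligible patients in all three arms, by a number the documents do not give. If the investigator judges the active-only rule safe, keep Table 3 and correct the Table 5 sentence together with the risk justification that relies on it. That costs no patients.

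**Cardiovascular disease.** If Table 5 was meant as shorthand, replace its sentence with the four Table 3 items, at no cost in patients. If the wider exclusion was intended, define it fully in Table 3 and the screening form, including whether stable coronary disease, arrhythmia and controlled hypertension count. Adding only arrhythmia and heart failure would not make the two tables match. The wider exclusion would reduce eligibility by an amount that cannot be derived from the documents.
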